9.2 Protocol Deviations

Protocol deviations that could potentially affect the safety conclusion of the study will be identified prior to database lock.

A listing of all protocol deviations including the deviation designation (major or minor) and category will be presented in a data listing.

Major protocol deviations will be summarized by deviation category (ie, compliance, prohibited medication, etc.) and INS-212 treatment arm.

9.3 Demographic and Baseline Characteristics

Demographic variables include: country, age, sex, ethnicity and race. Age will be calculated in years relative to the informed consent date in INS-212. Demographic variables will be summarized by geographic region and overall. Descriptive statistics will be presented for age. Frequency counts and percentages will be presented for region, country, sex, ethnicity, race and stratification criteria.

Eligibility criteria (inclusion/exclusion) not met by subjects who screen failed will be presented in a listing.

Enrolled subjects who are eligible but excluded from the safety population will also be listed.

9.4 Medical History and Medical Conditions Present at Entry

Ongoing Medical History and/or adverse events that are continuing from INS-212 will be collected in Medical History eCRF page. All adverse events (AEs) that occur between the time a subject signs the informed consent for INS-312 and receives his/her first dose in INS-312 will be considered as medical history and not as an AE unless the event worsens in severity after treatment start. The general medical history will be summarized by System Organ Class and preferred term.

9.5 Concomitant Medications

Concomitant medications are those medications taken on or after the first dose (Day 1) of study drug in INS-312. All ongoing medication(s) that were recorded in INS-212 prior to the first dosing in INS-312 will be considered as concomitant medications in INS-312.

Concomitant medications will be summarized for each INS-212 treatment arm by World Health Organization (WHO) Drug Dictionary (WHODDE B2 format, September 2016) Anatomical/Therapeutic/Chemical (ATC) classes ATC1 (Anatomic) and ATC2 (Therapeutic). These summaries will present the number and percentage of subjects using each medication. Subjects may have more than one medication per ATC class and preferred

name. At each level of subject summarization, a subject is counted once if he/she reported one or more medications at that level. Each summary will be ordered by descending order of incidence of ATC class and preferred name within each ATC class. The tables for medications will be sorted by decreasing frequency of ATC1 followed by ATC2 based on the total incidence across treatment arms. In case of equal frequency regarding ATC1 (respectively ATC2), alphabetical order will be used. Prior medications will be summarized for overall subjects by WHO ATC classes ATC1 (Anatomic) and ATC2 (Therapeutic) similarly to concomitant medications.

10. SECONDARY AND EXPLORATORY EFFICACY ANALYSES

All efficacy analyses will be based on the safety population.

The change from baseline (Day 1) in the EQ-5D-3L subject reported health outcomes to all study visits. The EQ-5D-3L consists of two parts. One is a descriptive system of questions and the other an EQ visual analogue scale (EQ-5D-VAS) measurement. The EQ-5D-3L descriptive system is comprised of 5 dimensions: mobility, self-care, usual activities, pain/discomfort and anxiety/depression. For each dimension the response has 3 levels: no problems, some problems, extreme problems. A single index score will be calculated from the response for the 5 dimensions. The index score will be calculated using United Kingdom weights. The algorithm for index value derivation is provided by the EuroQol Group Foundation [1]. The EQ-5D-3L index scores ranges from 0 to 1; 0 meaning death and 1 complete health. The EQ-5D-VAS records the respondent's self-rated health on a vertical, visual analogue scale where the endpoints are labelled 'Best imaginable health state' and 'Worst imaginable health state'. This information will be used as a quantitative measure of health outcome as judged by the subjects.

CT Scan (substudy)

For subjects participating in the CT scan sub-study, CT scan results will be qualified as ‘normal’, ‘abnormal – not clinically significant’ or ‘abnormal – clinically significant’ at baseline and ‘improved’, ‘worsened’ or ‘no change from previous’ at post-baseline assessments. The number and percent of subjects within each CT scan category will be summarized by scheduled visits.

Subject reported symptoms of Nontuberculous Mycobacteria:

The incidence of subjects who reported symptoms of NTM lung infections caused by MAC that are refractory to treatment will be summarized by scheduled visits.

10.2 Baseline Values

Last non-missing value on or before the first dose of study medication in INS-312 study will be used as the Baseline. An unscheduled visit may be used in the determination of baseline values, if it provides the last non-missing value prior to the first dose of the study drug in study INS-312.

10.3 Adjustments for Covariates

No adjustments for covariates are planned.

10.4 Handling of Dropouts or Missing Data

The handling of missing sputum culture results is built into the determination of whether a subject achieves culture conversion. For each culture conversion endpoint, all subjects are classified as either a converter or a non-converter. Refer to [Section 10.1](#) for details.

For all other endpoints, missing data will not be imputed and will be considered as missing in statistical analyses.

10.5 Examination of Subgroups

No subgroup analyses are planned.

10.6 Adjustments for Multiple Testing

No adjustments for multiple testing are planned.

10.7 Multicenter Studies

The study will enroll subjects at approximately 150 sites in North America, Europe, and Asia-Pacific regions. Thus, the number of subjects per site will be small. No investigation of site effect is planned and site will not be included as a factor in any analyses.

11. METHODS OF EFFICACY ANALYSIS

Unless otherwise stated, the safety population will be used for all efficacy analyses. For all efficacy data (Sputum Culture Conversion, 6MWD, SGRQ, EQ-5D-3L and Subject reported symptoms of NTM) observed values and changes from Baseline for continuous variables, absolute and relative frequencies for categorical observations, and shift tables from Baseline to last observation will be summarized overall and by the treatment group in INS-212 using descriptive statistics.

Time to Culture Conversion:

Time to culture conversion is defined in [Section 10.1](#).

Kaplan-Meier curves of the percentage of subjects achieving conversion will be determined for each of the two INS-212 treatment arms and presented in a figure. Also, the median time to conversion together with the 25th and 75th percentiles and their associated 95% Confidence intervals (CIs) will be presented for the two INS-212 treatment arms.

The following lines provide sample SAS code for the Kaplan-Meier curves and estimates.

```
PROC LIFETEST DATA = INPUT_DATA METHOD = KM;  
    TIME MONTHS * CENSOR (1);  
    STRATA TRT;
```

MONTHS is the number of months, rounded to the nearest integer, to culture conversion (based on either the date of conversion or the date of censoring). TRT is the treatment and CENSOR is an indicator variable that indicates whether conversion occurred (CENSOR = 0) or censoring occurred (CENSOR = 1).

12. PHARMACOKINETIC ANALYSES

Not applicable.

13. SAFETY ANALYSES

All safety analyses will be based on the Safety population. All available data as of the data cut-off will be used in the safety analyses.

13.1 Extent of Exposure and Compliance

Study drug exposure will be summarized for each INS-212 treatment arm and overall based on the total number of doses taken, the total number of doses missed, compliance and the duration of treatment. Number of doses taken, number of doses missed and compliance will be summarized by overall treatment period and by each visit (Month). Duration of treatment in months will be summarized for the 12-month treatment period. Duration of treatment is defined as the difference between the last dose date and the first dose date in INS-312 plus 1.

Study drug compliance will be calculated as follows:

- Compliance [%] = (Actual number of vials used)/(Prescribed number of vials to be used) × 100%
- Prescribed number of vials to be used = Number of days study medication is to be taken (based on the duration of treatment). At all visits, prescribed number of doses to be taken is the last visit date at that visit (month) minus the first visit date at that visit (month) minus 3 plus 1.
- The actual number of vial used is collected in the eCRF.

Study drug compliance will be summarized by INS-212 treatment arm and overall using counts and percentages as categorized below:

- >120%
- $80\% \leq \text{compliance} \leq 120\%$
- <80%

13.2 Adverse Events

All AE summaries will be restricted to treatment-emergent AEs (TEAEs), which are defined as those AEs that occurred on or after the date of first dose of study medication in INS-312 and within 28 days after the last dose. If it can't be determined whether the AE is treatment emergent due to a partial onset date, then it will be classified as treatment emergent. All ongoing AEs from the INS-212 study will be documented as medical history for INS-312. At visits where study drug is administered, the occurrence of AEs will be assessed before and after administration of study drug. Any AE that has occurred before administration of the study drug on Day 1 in INS-312 and was resolved will be documented

for study INS-212. Verbatim terms on eCRFs will be mapped to preferred terms and system organ classes using the Medical Dictionary for Regulatory Activities (MedDRA).

Each AE summary will be displayed by INS-212 treatment arm and overall. Summaries that are displayed by system organ class and preferred terms will be ordered by descending order of total incidence of system organ class and preferred term within each system organ class. Summaries of the following types will be presented:

- Overall summary of TEAEs.
- Subject incidence of TEAEs and total number of TEAEs by MedDRA system organ class and preferred term.
- Subject incidence of most common ($\geq 5\%$) TEAEs and total number of TEAEs by MedDRA system organ class and preferred term.
- Subject incidence of serious TEAEs and total number of serious TEAEs by MedDRA system organ class and preferred term.
- Subject incidence of TEAEs and of serious TEAEs adjusted for exposure by MedDRA system organ class and preferred term. Subject-years incidence will be computed as the number of subjects who experienced the event during the study divided by the cumulative number of years all subjects were active in the treatment arm. For those subjects in the study at the time of data base cutoff (as example, for DMC review), their years in study will be censored at the time of database cutoff. To adjust for per 1,000 subject-years of exposure, the resulting incidence rate will be multiplied by 1,000.
- Subject incidence of TEAEs by MedDRA system organ class, preferred term, and common terminology criteria for adverse events (CTCAE) severity grade (i.e., 1 to 5). At each level of subject summarization, a subject is classified per the highest severity if the subject reported one or more events. AEs with missing CTCAE severity grade will be considered as having missing CTCAE severity grade.
- Subject incidence of TEAEs by MedDRA system organ class, preferred term, and closest relationship to study drug (Related/Not Related). Related AEs are those reported as “Definitely”, “Probable”, or “Possibly”. At each level of subject summarization, a subject is classified per the closest relationship if the subject reported one or more events. AEs with a missing relationship will be considered as having missing relationship.
- Subject incidence of serious TEAEs by MedDRA system organ class, preferred term, and closest relationship to study drug (Related/Not Related). Related AEs are those reported as “Definitely”, “Probable”, or “Possibly”. At each level of subject summarization, a subject is classified per the closest relationship if the subject reported one or more events. AEs with a missing relationship will be considered as having missing relationship.

- Subject incidence of TEAEs leading to death as an outcome by MedDRA system organ class and preferred term
- Exposure adjusted subject incidence of TEAEs leading to death as an outcome and by MedDRA system organ class and preferred term. Subject-years exposure adjusted incidence rate will be calculated the way it is described above.
- Subject incidence of TEAEs leading to study drug withdrawn and Multi-Drug Regimen for NTM withdrawn by MedDRA system organ class and preferred term.
- Subject incidence of serious TEAEs leading to study drug withdrawn and Multi-Drug Regimen for NTM withdrawn by MedDRA system organ class and preferred term.
- Time to first serious adverse event (SAE) by Treatment Arm will be summarized using Kaplan-Meier curves and estimates. Median time together with the 25th and 75th percentiles and associated 95% CI will be presented by treatment arm as well as the number and percentage of censored observations. Time will be censored at the date of last contact on or before EOS for each subject who didn't have any SAE. If there are insufficient SAEs only the summary table will be provided.

All information pertaining to AEs noted during the study will be presented in a subject listing. In addition, serious TEAEs, TEAEs leading to death and TEAEs leading to drug withdrawn will be shown in one or more separate subject listings.

13.3 Clinical Laboratory Evaluation

Laboratory parameters (hematology and chemistry) will be summarized using descriptive statistics at baseline and at each post-baseline time point. Changes from baseline will also be summarized. Baseline is defined as the last non-missing value prior to first dose of study drug in INS-312. Descriptive statistics at baseline and change from baseline is limited to continuous data. Laboratory parameters summary will be displayed by INS-212 treatment arm and overall.

Shift tables (ie, low-normal-high at baseline versus low-normal-high at follow-up in a 3-by-3 contingency table) will be provided to assess changes in laboratory values from baseline to each post-baseline visits. Reference ranges established by the central lab will be used to determine shifts. Determination of clinical significance for all out-of-range lab values will be made by the Investigator.

The numbers and percentages of subjects with clinically significant abnormal laboratory values will be summarized by each visit.

Clinical laboratory results will be provided in subject listings.

13.4 Vital Signs

Vital signs (body weight, BMI, blood pressure, pulse rate, body temperature, respiratory rate and oxygen saturation) will be summarized using descriptive statistics at baseline and at each post-baseline time point. Changes from baseline will also be summarized. Baseline is defined as the last non-missing value prior to first dose of study drug in INS-312. Vital sign parameters summary will be displayed by INS-212 treatment arm and overall.

All vital sign results will be shown in subject listings.

13.5 Physical Examination

Physical examination results will be included in subject listings only.

13.6 Audiology Test

Audiology (by each ear and frequency) will be summarized using descriptive statistics at baseline, Month 6 and Month 12 (EOT). Changes from baseline will also be summarized. Baseline is defined as the last non-missing value prior to first dose of study drug in INS-312. Audiology test summary will be displayed by INS-212 treatment arm and overall.

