##### **7.1.6.2 Assessment**

Significant findings that meet the definition of an AE (including hearing loss of a CTCAE Grade 2 or higher) must be recorded on the AE page of the eCRF. Any significant finding that has occurred before administration of the study drug on Day 1 (Baseline) will be documented for study INS-212.

Protocol Amendment 3.1: 25 May 2017

*This protocol is solely for communicating information about the investigational drug between Inmed Incorporated and study personnel. Information is not to be reproduced, abstracted or used for sharing of information for any other purpose, whatsoever, except with the written permission of Inmed Incorporated.*

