## 8.3 ADVERSE EVENTS OF SPECIAL INTEREST

Adverse events of special interest (AESI) are those known to be attributed to parenteral amikacin:

- nephrotoxicity, including elevation of serum creatinine, albuminuria, presence of red and white cells, casts, azotemia, and oliguria
- ototoxicity affecting the eighth cranial nerve resulting in hearing loss, loss of balance, or both.
- neuromuscular disorders
- allergic alveolitis
- bronchospasm
- hemoptysis

Cough is often associated with drug products that are nebulized. To properly characterize AEs of cough, specific details regarding AEs of cough will be reported in the AE eCRF pages.

It is expected that subjects in this study will experience a large number of pulmonary exacerbation events due to their underlying lung condition(s). Pulmonary exacerbation will be defined based on the Investigators best clinical judgment. Details of the type of exacerbation should be provided on the AE eCRF.

Protocol Amendment 3.1: 25 May 2017

*This protocol is solely for communicating information about the investigational drug between Inmed Incorporated and study personnel. Information is not to be reproduced, abstracted or used for sharing of information for any other purpose, whatsoever, except with the written permission of Inmed Incorporated.*

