6.4.8. CTC Grading of Audiology Results

Hearing loss will be graded based on the CTC grading criteria in [Table 3](#) .

Table 3: Hearing Loss CTC Grade

Grade	Criteria
1	Threshold shift of 15 - 25 dB averaged at 2 contiguous test frequencies in at least one ear.
2	Threshold shift of >25 dB averaged at 2 contiguous test frequencies in at least one ear.
3	Threshold shift of >25 dB averaged at 3 contiguous test frequencies in at least one ear; therapeutic intervention indicated.
4	Decrease in hearing to profound bilateral loss (absolute threshold >80 dB hearing loss at 2 kHz and above); non-serviceable hearing.

The baseline hearing test is the threshold for deriving the grade. Subjects who do not meet any of the above CTC grades will have a CTC grade of zero (0).

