7. GENERAL ANALYSIS CONSIDERATIONS

The statistical analyses will be reported using summary tables, listings, and figures, with subjects classified per their assigned INS-212 treatment. The ICH numbering convention will be used for all outputs. Unless otherwise noted, all statistical testing (if any) will be two-sided and will be performed at the 0.05 significance level. Tests will be declared statistically significant if the calculated p-value is < 0.05 .

Continuous variables will be summarized with means, standard deviations, medians, minimums, and maximums. Categorical variables will be summarized by counts and by percentage of subjects in corresponding categories. All data that meaningfully contribute to the objectives of the study will be included. Footnotes will specify the basis for the percentages. For percentages of subjects, the denominator will generally be the number of subjects in the analysis set and INS-212 treatment arm. All summary tables will be presented by INS-212 treatment arm. A total summary column may be included in some summary tables where relevant.

Summaries of continuous variables that have some values recorded using approximate values (eg, $<$ or $>$) will use the numeric part of the value in calculations. Listings will present the data in its original format.

For summaries where rounding is required, rounding will be done to the nearest round-off unit. For example, if the round-off unit is the ones place (ie, integers), values $\geq XX.5$ will be rounded up to $XX+1$ while values $< XX.5$ will be rounded down to XX .

Individual subject data obtained from the electronic case report forms (eCRFs), and any derived data will be presented by site, INS-212 treatment arm and subject in data listings.

Post-baseline unscheduled visit data will be presented in the listings only (ie, unscheduled visit data will not be summarized in tables). If a subject has more than one observation at a visit for any reason, the average of the observations will be used in summary tables.

The analyses described in this plan are considered a priori, in that they have been defined prior to database lock. Any other analyses performed will be considered post-hoc. Post-hoc analyses will be labeled as such on the output and identified in the CSR.

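### The SAP for the accelerated submission derives no per-subject hearing-loss grade or shift from the audiograms, so the first analysis has no audiogram-based count of subjects with hearing loss

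*SAP*

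**What the plan says.** The SAP file holds two plans: the final SAP and, after it, the SAP for the accelerated submission (here the first-analysis SAP).

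- **First-analysis SAP 13.6.** "Audiology (by each ear and frequency) will be summarized using descriptive statistics at baseline, Month 6 and Month 12 (EOT"). Changes from baseline are added, by INS-212 arm and overall. There is no grade, no shift table and no count of subjects.
- **First-analysis SAP 7.** This fixes what descriptive statistics means: "Continuous variables will be summarized with means, standard deviations, medians, minimums, and maximums". It also sends individual data to listings: "any derived data will be presented by site, INS-212 treatment arm and subject in data listings".
- **Protocol 8.3.** The adverse events of special interest include "ototoxicity affecting the eighth cranial nerve resulting in hearing loss, loss of balance, or both". Protocol 3.2 makes events of special interest part of the primary endpoint.
- **Protocol 7.1.6.2.** "Significant findings that meet the definition of an AE (including hearing loss of a CTCAE Grade 2 or higher) must be recorded" on the adverse event page.
- **First-analysis SAP 13.2.** "Subject incidence of TEAEs by MedDRA system organ class, preferred term, and common terminology criteria for adverse events (CTCAE) severity grade", each subject counted at the highest grade.
- **Final SAP 6.4.8, Table 3.** Grade 1 is a shift of 15 to 25 dB; Grade 2 is "Threshold shift of >25 dB averaged at 2 contiguous test frequencies in at least one ear". Section 9.7 tabulates subjects by grade 0 to 4, and tables 14.3.11.2 and 14.3.11.3 give hearing loss and shifts by visit.
- **Shift tables.** The Protocol synopsis (Statistical Methods) includes audiology among the safety data to be shown in shift tables from baseline to last observation. Protocol 9.6 repeats the sentence without audiology. First-analysis SAP 14 declares no changes from the protocol-specified analyses.

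**The concern.** Drug-induced hearing loss happens to individuals, and the protocol judges it that way: by CTCAE grade, per subject, with a repeat test at the next visit after a Grade 2 or higher finding (Protocol 7.1.6.1). The first-analysis SAP instead treats audiometry as 12 separate continuous variables (2 ears by 6 frequencies). None of these can be turned into a number of subjects with hearing loss.

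Laboratory data in the same SAP (13.3) get both shift tables and counts of subjects with clinically significant values. Audiometry, which measures a named harm directly, gets neither. At stake is whether the accelerated submission carries an objective frequency of hearing loss or only the frequency that investigators chose to report.

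**Working it through.** The documents give no figure for audiology, so there is nothing to reproduce. The check has three parts.

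**1. What each route in the first analysis can count**

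| Finding on the audiogram | Continuous tables (13.6) | TEAE tables (13.2) | Listings (7) |
|---|---|---|---|
| Grade 2 or higher, reported as an AE | not counted | counted, by preferred term | shown |
| Grade 2 or higher, not reported | not counted | missed | thresholds shown, ungraded |
| Grade 1 (15 to 25 dB) | not counted | only if the investigator judges it an AE | thresholds shown, ungraded |

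The TEAE route has a further limit. Section 13.2 has no summary of events of special interest and no ototoxicity group. In Table 6 of the final SAP, hearing loss falls under six preferred terms: deafness, deafness bilateral, deafness neurosensory, deafness unilateral, hearing impaired and hypoacusis. Without grouping, no single line gives the number of subjects with hearing loss. The organ-class line also takes in tinnitus.

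**2. How the planned statistics respond to an effect in a minority**

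Assumptions, none from the documents except N: N = 200 (the expected enrolment); a fraction f shifts by s dB at one ear and frequency; the rest change by 0 on average; SD of change is sd. Then mean change = f × s, and SD = √(sd² + f(1 − f)s²). Median and maximum come from simulation (1,000 replicates).

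| f | s (dB) | sd (dB) | Affected | Mean | SD | Median | Maximum | Maximum, nobody affected |
|---|---|---|---|---|---|---|---|---|
| 5% | 30 | 5 | 10 | 1.5 | 8.23 | 0.36 | 37.7 | 13.7 |
| 5% | 30 | 10 | 10 | 1.5 | 11.95 | 0.67 | 45.5 | 27.4 |
| 10% | 30 | 5 | 20 | 3.0 | 10.30 | 0.72 | 39.4 | 13.8 |
| 10% | 30 | 10 | 20 | 3.0 | 13.45 | 1.39 | 48.6 | 27.5 |
| 10% | 40 | 5 | 20 | 4.0 | 13.00 | 0.69 | 49.3 | 13.8 |
| 20% | 20 | 5 | 40 | 4.0 | 9.43 | 1.61 | 30.8 | 13.7 |

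First row: mean = 0.05 × 30 = 1.5; SD = √(25 + 0.05 × 0.95 × 900) = √67.75 = 8.23. Over 2% to 20% affected and 20 to 40 dB, the mean runs from 0.02 × 20 = 0.4 to 0.20 × 40 = 8.0 dB.

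So mean and median dilute the effect, while SD and maximum respond to it. The last two rows share a mean of 4.0 dB, yet one has 20 subjects with shifts in the Grade 2 range and the other 40 in the Grade 1 range. The noise SD is unknown, so the reported SD cannot be turned back into a count.

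**3. Why the maximum is not a substitute for the grade**

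The grade averages two adjacent frequencies. A subject with a 40 dB shift at one frequency and 0 at its neighbours averages (40 + 0)/2 = 20 dB, Grade 1. A subject with 30 dB at two adjacent frequencies averages 30 dB, Grade 2 or higher. The per-frequency maximum ranks these two the wrong way round, and the maxima in the 12 cells may come from different subjects.

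**The case against.** A reader might infer that hearing loss in a minority would be averaged away, or that hearing would contribute no frequency at all to the accelerated submission. The documents do not support that. Section 13.6 is not limited to means: SD, median, minimum and maximum of value and change are planned, subject data are listed, and in the illustration the maximum rises well above its no-effect value. More important, Grade 2 or higher loss must be recorded as an adverse event and is then tabulated per subject by CTCAE grade. A subject with such a loss, duly reported, is counted.

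It can also be said that the final SAP already contains the grade tables, and that the first analysis is finished: final SAP 5.1 says it was performed on data cut on 07 July 2017. Both are true. The final tables serve the final analysis, and the earlier SAP governs the earlier one, so the gap in the first analysis stays open. The remedy is then a supplementary table or a declared omission.

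The illustration is indeed invented apart from N, and even N is generous. Subjects enter at the scheduled INS-212 Month 8 visit and have the first scheduled post-baseline audiogram six months later, while the cut was set by the last INS-212 Month 6 visit. The number with a post-baseline audiogram by then is not given.

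**Conclusion.** The point holds in a limited form. The first analysis has continuous audiometry summaries and adverse-event counts, but no frequency of hearing loss derived from the audiogram. Uncounted are Grade 1 shifts that are not reported as events, and Grade 2 or higher shifts that the investigator did not report. Reported Grade 2 or higher losses are counted, but scattered over preferred terms. The documents give no way to estimate how many subjects this involves; the 0.4 to 8.0 dB range shows only how little the mean would reveal.

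The conclusion assumes that the CTC criteria in Table 3 of the final SAP are those meant by the protocol's reference to CTCAE version 4.0, which gives no thresholds. The conflict over shift tables stands apart from the illustration: the synopsis names audiology, Protocol 9.6 does not, and the first-analysis SAP has no audiology shift table while declaring no changes. The gap is worth closing because ototoxicity is a named event of special interest within the primary endpoint. It does not show that the safety conclusion is wrong.

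**What to change.** 1. Apply the Table 3 grading of the final SAP to the first-analysis audiograms, using the pre-dose test as reference. Report number and percent of subjects by grade at Month 6 and at the worst post-baseline test, plus the shift table, overall and by INS-212 arm, with evaluable subjects as denominator. The worst-test row brings in repeat tests made after a Grade 2 finding, which fall outside the visits named in 13.6.
2. Set the derived grades beside the hearing events reported on the adverse event page and list the subjects on whom they disagree.
3. Reconcile the Protocol synopsis, Protocol 9.6 and first-analysis SAP 14 on audiology shift tables. If the first analysis is not re-run, declare the omission in the study report.
4. Keep the continuous tables as support.

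The cost is one derived variable and a short set of tables from audiograms already collected. The derivation is specified in the final SAP; the documents do not show that it had been programmed. One limitation: the grade takes the worst of 5 adjacent frequency pairs in each of 2 ears, so test-retest noise will yield some Grade 1 results by chance. Show Grade 1 separately from Grade 2 or higher.
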